### **Field Arrangements and Treatment Planning:**

An optimized 3-D conformal proton plan will be designed in consultation with the treating physician. Whenever possible multiple fields will be designed to limit the dose to normal tissues and critical structures and promote symmetric bone growth/retardation where applicable.

An optimized IMRT comparison photon plan will also be generated for the first 79 patients. Appropriate measures such as cerrobend blocks or MLCs will be fabricated or programmed so that the patient can be treated with photons in the event of an equipment malfunction rendering proton therapy unavailable. A patient may receive up to 25% of the prescription dose with photons provided the normal tissue tolerance limits are respected. In addition, this photon plan will serve as a comparison of doses to normal surrounding organs in the form of Dose Volume Histograms. A comparison of normal tissue doses will be made between the two plans as a primary objective of this study.

**Dose Specification and Schedule:**

The dose given to a particular sarcoma depends on the setting and the histological subtype. Schema for radiation dose prescription and fractionation schedule is outlined in the current IRS protocols (D9803, D9602, D9802) available on the COG website or by contacting either [name] [contact]), [name] [contact]) or [name] [contact]). Patients typically will be treated once per day, 5 days per week unless otherwise specified by a co-existing protocol. For those patients not on a national protocol the current accepted standard of care doses will be used which are based on IRS IV and IRS V data. Standard fractionation will be used to minimize late toxicity and maximize efficacy, 1.8-2.0 Gy per fraction. Typical doses are 36 Gy, 41.4 Gy, 45 Gy and 50.4 Gy depending on the circumstances.

Each proton field is normalized individually to usually the 97 to 100% isodose line. Doses will be prescribed to the appropriate isodose line encompassing the CTV such that the gradient within a volume is +7% to -5%. Dose will be reported in CGE, Cobalt Gray Equivalent (where 1 CGE = proton dose Gy x RBE [radiobiological effective dose], RBE = 1.1). An RBE of 1.1 has been selected for protons and is based on RBE determinations in animal and cell culture systems[21,22]. Patients will not receive doxorubicin or actinomycin-D concurrent with radiotherapy unless explicitly required by a national protocol.

**Proton beam physical factors:**

The FHBPTC cyclotron at MGH produces a 230 MeV proton beam. The synchrotron at MDACC produces a 250 MeV proton beam. The energy can be degraded to an appropriate energy to treat the desired depth. The SAD (Source to Axis Distance) at MGH is 2.27 meters; the SAD at MDACC is 2.7 meters.

**Proton Beam modification / Blocking:**

Beam shaping will be accomplished using primary collimation by the gantry jaws. The penumbra is large and field shaping by secondary collimation will be necessary using a downstream custom cut brass aperture. Tertiary collimation can be applied by installing a cone to hold a second brass aperture downstream from the 1st aperture. Apertures will be constructed on brass alloy of sufficient thickness to attenuate 100% of protons. 3-D lucite compensators are fabricated to conform dose to the target at the distal aspect.

## **Quality Assurance:**

### *Beam verification:*

Pre-treatment port films should be compared with a digitally reconstructed radiography (DRR) constructed from the treatment planning system. Film or digital images will be taken in accordance with the proton center's standard practice for all patients. These images are used to verify the position of the patient and the aperture.

### *Dose Uniformity:*

Dose gradient in CTV should remain within +7% to -5% of prescribed dose.

### *Dose verification:*

A physicist will be responsible for dose verification.

### *Rapid Review of Treatment Plans:*

To ensure protocol compliance, the treatment plans for the first three patients treated at each site will be reviewed by the Principal Investigator and Participating Site's PI.

## **Concurrent Protocols and Which Radiation Therapy Guidelines to Follow:**

For patients who are enrolled on co-existing protocols such as COG, physicians will adhere to the radiation therapy guidelines of the companion protocol which specify their own guidelines for the following parameters: total dose, dose per fraction, fractionation schedule and sequencing with other therapy (e.g. chemotherapy). If any questions or discrepancies arise, then contact. [name] at [contact] ([contact]), [name] [contact] ([contact]) or [name] [contact] or [contact]) before beginning radiation treatments.

## **Treatment Delay:**

To avoid treatment delays resulting from the machine being down, photon beam radiation can be administered. The maximum dose delivered by photons will be 25% of the prescribed dose. Treatment delays will be allowed if a serious adverse event occurs due to protocol therapy. Treatment delays will also be allowed for patients who experience a serious adverse event not related to protocol therapy (e.g. concurrent chemotherapy requiring hospitalization for neutropenia).

## **VI. BIOSTATISTICAL ANALYSIS**

Primary outcomes are acute and late complications following proton beam irradiation to the tumor or tumor bed. Late complications are defined as the delayed effects attributable to radiation which occur > 90 days following completion of radiation, while acute side effects are those occurring during radiotherapy or up to 90 days after the last dose. Allowing for 5% inflation for unevaluable patients due to ineligibility or early dropout, the revised accrual goal is a total of 115 patients with a minimum follow-up of another 2

years following the patient enrollment for observing the late complications of proton beam irradiation.

The goal of utilizing protons is an improvement in the historical complication rate, which varies by site and type of complication. The literature for parameningeal or other head and neck rhabdomyosarcomas has reported endocrine effects occurring in 50-100% and impaired orbital function in 70-100% of patients (23-27). For children treated for pelvic tumors, late effects were significantly higher among patients treated, ranging from 54% to 77% (28). Across all anatomic sites, the likelihood of one or more reported late effects has been approximately 70% or more among those who received conventional radiation. Among a total of 110 patients, the probability is 81% that 70 or fewer of them will develop any late effect if the overall complication rate is truly decreased to 60% with the use of protons. The decision rule is associated with only 9% probability if the underlying rate were truly similar to the 70% historical rate observed with conventional radiation.

Due to a difference in the radiation doses used for treating patients with different tumor characteristics (typical doses are 36 Gy, 41.4 Gy, 45 Gy and 50.4 Gy), the outcomes will be analyzed according to dose group,  $\leq$  45 Gy and  $\geq$  45 Gy. Data on the enrolled patients shows a 1:4 ratio in the distribution of patients receiving low versus intermediate radiation doses. Constitutional symptoms, namely fatigue and malaise, as well as skin reactions in the radiation port will be analyzed according to dose group.

As rhabdomyosarcoma may occur at almost any site, many of the side effects will be determined by the range of tumor location. Thus analysis of tissue-specific toxicities has depended typically on relatively small patient numbers and was limited generally to descriptive statistics. Moreover, subgroup analysis of acute symptoms may be confounded by the type of concurrent chemotherapy. Accrual has been increased to obtain reasonable precision for the estimation of tissue-specific toxicities associated with the most common tumor sites, especially late effects arising during long-term follow-up. Patients will not be evaluable for late effects following treatment failure in local, regional and/or metastatic sites, development of a secondary malignancy or death due to any cause. In particular, projection of the current patient distribution indicates the increased accrual will comprise 56 patients with parameningeal tumors and 24 patients with orbital sarcomas. These expected numbers are associated with 95% exact confidence intervals of maximal width  $\pm$  14% and  $\pm$  22%, respectively. The corresponding numbers evaluable for late effects are projected to be 42 and 18 patients based on the five-year event-free survival of 69% observed among the first 57 protocol patients. The maximal interval widths are  $\pm$  17% and  $\pm$  25%, respectively, at five years following proton radiotherapy. We also expect to enroll 3-6 patients with each of the rare tumor sites (non-parameningeal head and neck, trunk, prostate/bladder, extremity, perineal/anal and liver/biliary tract regions).

All toxicity grading will be coded according to the COG/RTOG scales provided in the appendices. Toxicities and events not listed in these scales will be graded according to the Common Terminology Criteria for Adverse Events (CTCAE), Version 3.0. Many patients are expected to be co-enrolled on COG protocols comparing chemotherapy

regimens. Since interim analysis will be performed on the parent COG protocols and any action taken will impact directly on the proton protocol, no formal sequential monitoring of efficacy is planned within this protocol.

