**Source of subjects and recruitment methods:**

Approximately 320 cases of pediatric rhabdomyosarcoma are diagnosed in the US per year[1]. Patients have been coming to MGH from all over the United States to be treated with proton irradiation and this trend is likely to continue. Patients will be recruited from MGH, BWH, Boston Children's Hospital, DFCI and MD Anderson Cancer Center. We estimate an annual accrual of 10 pediatric sarcoma patients across all participating sites, for a total accrual of 80 patients. Proton radiotherapy will be listed on the MGH Proton Center web site as a formal protocol and information of its availability will be made known to treating professionals through group (COG) meetings.

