**Late toxicity (Site specific):**

Late toxicity is to be scored on a yearly follow-up basis for at least five years. Ten years is suggested but not required. Additional tests may be required as clinically indicated. Late toxicities will be graded according to the Common Terminology Criteria for Adverse Events (CTCAE), Version 3.0.

*General studies at yearly follow-up visits:*

1. History and Physical exam
2. Weight and height

*Head and Neck:*

- Neuro-psychiatric evaluation every other year (+/- 12 months) if >20% of the whole brain received 10% of the prescribed dose as determined by the radiation oncologist evaluating the treatment plan.
- Endocrine labs recommended to be drawn annually if the dose to the pituitary or hypothalamus received 20 Gy RBE or more, or if the whole thyroid was included in the radiation port. Labs include TSH, Free T4, Cortisol (AM value), IGF-1, IGF-BP3, LH, FSH, prolactin, estradiol (females) or testosterone (males).

*Orbit:*

- Annual ophthalmologic exam to be completed (+/- 6 months) if the orbit is in the involved field.

*Ear or middle ear involvement*

Annual audiometric exams with word recognition must be completed (+/- 6 months) if the mean radiation dose to the cochlea received 20 Gy RBE or more, or in patients in which the tumor involved one or both of the 8th cranial nerves. The word recognition portion of the exam will be administered to age and developmentally appropriate children, generally age 4 and over.

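### Late-effect precision is stated at five years, but Section VI sets only a 2-year minimum follow-up and does not say when the five-year analysis is done; at the 2-year minimum the stated widths are not reached.

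*Combined protocol and SAP*

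**What the plan says.** Section VI (Biostatistical Analysis) sets the size and follow-up of the study in one sentence: "the revised accrual goal is a total of 115 patients with a minimum follow-up of another 2". The unit is years, counted from enrollment, and the stated purpose is to watch for late complications. The 115 comes from 110 patients with a 5% allowance: "Allowing for 5% inflation for unevaluable patients due to ineligibility or early dropout".

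Section VI then explains that accrual was raised to improve precision for tissue-specific toxicities, late effects above all. It projects that "the increased accrual will comprise 56 patients with parameningeal tumors and 24 patients with orbital sarcomas", with maximal exact 95% interval widths of ±14% and ±22%. For late effects the two groups shrink to 42 and 18, on the basis of a five-year event-free survival of 69% in the first 57 patients. The widths become ±17% and ±25%, "at five years following proton radiotherapy". Patients stop being evaluable for late effects after treatment failure, a second malignancy or death.

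Two other places bear on follow-up. Under Late toxicity (Site specific) in Section IV: "Late toxicity is to be scored on a yearly follow-up basis for at least five years". Inclusion criterion 5 in Section III asks patients to accept at least five years of follow-up after treatment.

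The only accrual rate is in Section III, Source of subjects: "We estimate an annual accrual of 10 pediatric sarcoma patients across all participating sites, for a total accrual of 80 patients". No rate is given for the total of 115, and no section fixes a date or trigger for the late-effect analysis.

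**The concern.** The only follow-up period in Section VI is 2 years, and its stated purpose is to observe late complications. The precision quoted a few lines later is for five years. The step from 56 and 24 to 42 and 18 removes patients who have an event. It removes nobody for short follow-up, so it implicitly assumes that every event-free patient has already reached five years. Read together, the two statements would let the analysis be run at 2 years while still quoting five-year precision.

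Late complications are a primary outcome, and precision for the common tumor sites is the stated reason for enrolling more patients. If the widths apply only to an analysis date that the plan never sets, that justification is incomplete. The small orbital group has the most to lose.

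**Working it through.** **Inputs**
- Section VI: 115 patients; minimum follow-up 2 years from enrollment; 56 and 24 enrolled by site; 42 and 18 evaluable; five-year event-free survival 69%; stated widths ±14%, ±22%, ±17%, ±25%.
- Section III: 10 patients per year, given with a total of 80.
- Assumptions: steady accrual; both sites accrue evenly over time; the interval from enrollment to radiotherapy is ignored.

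**Step 1. Reproduce the plan's widths.** Clopper-Pearson 95% intervals, maximised over all outcomes 0 to n. There are two readings of maximal width: half the interval length, and the largest distance from the estimate to a limit.

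| n | half-width | largest distance | stated |
|---|---|---|---|
| 56 | 13.7% | 14.0% | 14% |
| 24 | 20.9% | 22.0% | 22% |
| 42 | 15.8% | 16.3% | 17% |
| 18 | 24.0% | 25.7% | 25% |

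Each stated figure is matched to within about one point on at least one reading. One side remark: 42/56 = 18/24 = 75%, whereas 69% gives 56 × 0.69 = 38.6 and 24 × 0.69 = 16.6. That is a separate matter, so both starting points are carried through below.

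**Step 2. Patients short of five years at the 2-year minimum.** (5 − 2) years × 10 per year = 30. 30/115 = 26%. The share with five years is 85/115 = 0.739.

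**Step 3. Evaluable patients at that cut-off.**
- From the plan's counts: 42 × 85/115 = 31.0 and 18 × 85/115 = 13.3, so about 31 and 13.
- From 69% directly: 38.6 × 85/115 = 28.6 and 16.6 × 85/115 = 12.2, so about 29 and 12.

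**Step 4. Widths at those numbers.**

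| n | half-width | largest distance | stated |
|---|---|---|---|
| 31 parameningeal | 18.4% | 19.1% | 17% |
| 13 orbital | 27.8% | 30.7% | 25% |
| 29 parameningeal | 19.0% | 19.8% | 17% |
| 12 orbital | 28.9% | 32.2% | 25% |

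**Step 5. Like-for-like change from the plan's own counts.**
- Parameningeal (42 to 31): 15.8% to 18.4%, or 16.3% to 19.1%; about 3 points.
- Orbital (18 to 13): 24.0% to 27.8%, or 25.7% to 30.7%; about 4 to 5 points.

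**Step 6. Sensitivity to the accrual rate (assumed 5 to 15 per year), from 42 and 18.**
- 5 per year: 15 short; share 100/115; n about 37 and 16; 16.8-17.4% and 25.3-27.4%.
- 15 per year: 45 short; share 70/115; n about 26 and 11; 20.1-21.1% and 29.9-33.7%.

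**Step 7. Analysis when all have passed five years.** Nobody is short, n stays at 42 and 18, and this loss is zero.

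**The case against.** The strongest reply is that 2 years is a minimum, not an analysis date. Nothing in the documents locks the data at that point. The quoted precision is labelled as five-year precision, criterion 5 asks for five years of follow-up, and late toxicity is scored for at least that long. On that reading the data will exist and the widths stand once the analysis waits. This is correct, and it limits the point to an unreconciled conflict. A reader might infer that five-year data cannot be obtained for 30 patients, and the documents do not support that. Equally, criterion 5 and the visit schedule govern data collection. They do not set analysis timing, and Section VI names no period other than 2 years.

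Other stronger readings also fail:
- That the projection counts everyone enrolled. It does not: 56 and 24 are cut to 42 and 18 for events.
- That 30 evaluable patients are lost. At 69% event-free survival, about 30 × 0.69 = 21 of them would have been evaluable, and the scaling in the working already allows for this.
- That the orbital estimate becomes worthless. The plan already accepts ±25%, and the loss is a few points.
- That the decision rule of 70 or fewer late effects in 110 patients is undermined. Its stated probabilities reproduce (80.9% at a true rate of 60%, 9.0% at 70%), and this point does not touch it.

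It can also be said that the loss arises only if patients with shorter follow-up are left out, and that a method using partial follow-up would lose less. That stands. Section VI, however, gives exact binomial intervals and does not say how partial follow-up would enter. A competing-risk cumulative incidence would use it, but that estimates a different quantity from the proportion affected among event-free patients, so its precision cannot simply replace the stated widths.

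**Conclusion.** The point holds conditionally. The 2-year minimum and the five-year precision in Section VI are not reconciled, and the evaluable counts make no allowance for patients with less than five years of follow-up. At the 2-year minimum, and at 10 patients per year, 30 of 115 patients fall short. The widths are then about ±18-19% against a stated ±17% (1 to 2 points worse) and ±28-31% against ±25% (3 to 6 points worse). The accrual rate belongs to a superseded total. At 5 per year the result is close to the stated widths, and at 15 per year it reaches about ±21% and ±34%.

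The figures rest on steady accrual, an even site mix over time and an analysis restricted to event-free patients with five years of follow-up. If the analysis waits for five years on every patient, there is no loss from this source. The affected widths are descriptive and drive no decision rule, but they are the stated reason for the larger accrual. This should be fixed.

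**What to change.** In Section VI, do one of the following:

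1. State that the five-year site-specific late-effect analysis is done when all patients have passed five years after radiotherapy, and reconcile the 2-year minimum with inclusion criterion 5 and the late-toxicity schedule, which already provide for that follow-up.
2. Or keep the 2-year cut-off and restate the evaluable numbers and widths for it, using an accrual rate that applies to 115 patients.

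If any five-year estimate is to be reported before everyone has reached five years, specify a censoring-adjusted cumulative incidence (Aalen-Johansen), with treatment failure, second malignancy and death as competing events. State that this is a different quantity from the proportion among event-free patients.

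The change is wording and a short recalculation, with no added patients or visits. The first option delays the five-year report, and the second shows a less favourable precision.

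### The late-effect rule of 70 or fewer of 110 assumes complete status for every patient and names no time point; under the plan's own evaluability rule its power is below the stated 81%

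*Combined protocol and SAP*

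**What the plan says.** All of the following is in the combined protocol and SAP.

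- **The rule (Section VI).** "Among a total of 110 patients, the probability is 81% that 70 or fewer of them will develop any late effect" if protons lower the true rate to 60%. For the null case: "The decision rule is associated with only 9% probability if the underlying rate were truly similar to the 70% historical rate".
- **The benchmark (Section VI).** "the likelihood of one or more reported late effects has been approximately 70% or more among those who received conventional radiation". No time frame is attached to it, and the text does not say whether it is a crude proportion of treated patients or a rate among those followed without failure.
- **The loss allowed for (Section VI).** "Allowing for 5% inflation for unevaluable patients due to ineligibility or early dropout", the accrual goal is 115, "with a minimum follow-up of another 2" years. No other loss is built into the 110.
- **Evaluability (Section VI, next paragraph).** "Patients will not be evaluable for late effects following treatment failure in local, regional and/or metastatic sites, development of a secondary malignancy or death" from any cause.
- **Where that loss is applied (Section VI).** Only to the parameningeal and orbital groups of 56 and 24: "The corresponding numbers evaluable for late effects are projected to be 42 and 18 patients based on the five-year event-free survival of 69" percent. The interval widths for these reduced numbers are given "respectively, at five years following proton radiotherapy".
- **Follow-up elsewhere.** Inclusion criterion 5 (Section III) and the late toxicity part of Section IV both ask for at least five years.

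**The concern.** Section VI makes two different assumptions about who can be assessed for late effects. The site-specific precision figures take off patients who fail, develop a second cancer or die. The overall rule, the only formal test of whether protons lower the late-effect rate, takes off none of them. A 5% allowance for ineligibility and early dropout cannot cover that loss when five-year event-free survival is 69%.

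The rule also refers to patients who will develop a late effect without saying by when. The 2-year minimum follow-up and the five-year horizon are both available, and the loss differs a good deal between them. Nor does the plan say how a patient who fails without a late effect enters the count. With time point, denominator and handling of failures all open, the same data could pass or fail according to choices made at analysis, and the stated 81% / 9% would not describe the test carried out.

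**Working it through.** **Inputs from Section VI.** n = 110, cut-off 70, rates 60% and 70%; five-year event-free survival (EFS) 69%; site projections 56 to 42 and 24 to 18. **Assumption:** the documents give no 2-year EFS, so exponential failure is used.

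**1. The plan's own figures.** Exact binomial:
- P(X ≤ 70 | 110, 0.60) = 0.809
- P(X ≤ 70 | 110, 0.70) = 0.0897

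Both match the stated 81% and 9%.

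**2. Number evaluable if patients who fail are dropped.**
- Five years, stated EFS: 110 × 0.69 = 75.9, about 76.
- Five years, the plan's own ratio: 42/56 = 18/24 = 0.75, and 110 × 0.75 = 82.5, so 82 or 83. (69% of 56 and 24 would be 38.6 and 16.6, so the plan's ratio and its cited EFS do not agree; both are carried.)
- 2 years: 0.69^(2/5) = 0.862, and 110 × 0.862 = 94.8, about 95.

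**3. Power with a whole-number cut-off.** The cut-off is the largest count whose probability at 70% rounds to 9% or less.

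| n | cut-off | error at 70% | power at 60% |
|---|---|---|---|
| 76 | 47 | 7.9% | 66.9% |
| 77 | 48 | 9.2% | 70.2% |
| 78 | 48 | 6.8% | 65.0% |
| 79 | 49 | 7.9% | 68.3% |
| 80 | 50 | 9.2% | 71.4% |
| 81 | 50 | 6.9% | 66.4% |
| 82 | 51 | 8.0% | 69.6% |
| 83 | 52 | 9.2% | 72.6% |
| 94 | 59 | 8.0% | 74.2% |
| 95 | 60 | 9.1% | 76.7% |
| 96 | 60 | 7.0% | 72.6% |

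The ups and downs come from whole-number cut-offs. Interpolating between adjacent cut-offs to exactly 9% error removes them: 69.1% at n = 76, 71.5% at 82, 72.2% at 83 and 76.4% at 95.

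**4. Sensitivity at 2 years.** If failures come earlier than exponential, fewer patients are evaluable. At 9% error, a 2-year EFS of 80% (n = 88) gives 73.8% power and 75% (n = 82) gives 71.5%.

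**5. Keeping 110 and counting patients who fail without a late effect as free of one.** Suppose 70% is the rate by time T in the absence of failure, with constant hazards: hL = −ln(0.30)/T for late effects and hF = −ln(EFS)/5 for failure. Then

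P(late effect before failure, by T) = hL/(hL + hF) × (1 − exp(−(hL + hF)T)).

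- T = 5, EFS 69%: hL = 0.2408, hF = 0.0742, probability 0.606; P(X ≤ 70 | 110) = 0.771.
- T = 5, EFS 75%: hF = 0.0575, probability 0.626; P(X ≤ 70 | 110) = 0.628.
- T = 2: hL = 0.602, probability 0.660 or 0.669; P(X ≤ 70 | 110) = 0.333 or 0.266.

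With late-effect onset varied (Weibull shape 0.7 to 1.5) the ranges widen to 0.49-0.90 at five years and 0.22-0.42 at 2 years. If the 70% is instead a crude proportion of treated patients, the probability stays at 0.70 and the error stays at 9.0%.

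**The case against.** **The stated figures are not wrong.** This stands: 81% / 9% is correct arithmetic for 110 complete patients. A reader might infer a calculation error; there is none. The difficulty is that the evaluability rule does not deliver 110 complete patients.

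**Non-evaluable following failure need not mean dropped altogether.** A late effect recorded before failure could still count, and the evaluability sentence sits in the paragraph on tissue-specific precision. This also stands, so the drop-out figures describe one reading. It does not restore 110 complete patients. Under the constant hazards of step 5, those who fail with no earlier late effect number 110 × hF/(hL + hF) × (1 − exp(−(hL + hF)T)): about 16-23 by five years and 7-10 by 2 years, at a true rate of 70% or 60% and EFS of 69% or 75%.

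**The 70% may be a crude proportion.** The plan describes it as reported late effects among those irradiated. If 60% and 70% are both crude rates on a matching time frame, a binomial on all 110 treated patients is the right model and 81% / 9% hold. A reader might infer from step 5 that the real false-positive rate is 63-77%. The documents do not support that: they do not define the benchmark's scale, and they nowhere propose counting patients who fail as free of late effects. They only leave it open.

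**The rule has a window.** The 2-year minimum is said to be for observing late complications. That is a minimum length of follow-up, not a time at which status is read, and the same section gives its late-effect precision at five years.

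**Conclusion.** The concern holds as a gap between the rule and the plan's own evaluability statement, together with a missing time point.

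- **Five years, patients who fail dropped (n = 76 to 83):** power about 69-72% at 9% error, or about 65-73% with whole-number cut-offs at 7-9% error. The 65% end belongs to 6.8% error (n = 78), not to 9%.
- **2 years (n about 95):** about 76% at 9% error. This rests on exponential failure, and power is lower if failures come earlier. The 76.7% at n = 95 is a favourable whole-number case; 94 and 96 give 74.2% and 72.6%.
- **All 110 kept, with failures counted as free of late effects:** the error exceeds 9% if the 70% is a rate absent failure. Its size depends on assumptions (constant hazards: about 63-77% at five years, 27-33% at 2 years). There is no inflation if the 70% is a crude proportion.

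A reader might also infer that the trial needs more patients. The documents do not support that: Section VI bases the increased accrual on precision for tissue-specific toxicities, not on this rule. This should be fixed, because it concerns a primary outcome and the correction is cheap.

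**What to change.** In Section VI:

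1. State one time point for the rule. Five years would match Sections III and IV and the site-specific intervals.
2. State the time frame and scale assumed for the 70% benchmark: crude among treated patients, or absent failure.
3. State that patients who fail without a late effect are not counted as free of late effects, using one method on the benchmark's scale. If the 70% is a rate absent failure, one example is a time-to-event estimate at the chosen time point, censored at failure, second malignancy or death, with improvement declared if the one-sided 91% upper limit is below 70%. Late effects recorded before failure then count.
4. If a count is kept, take both numerator and denominator from patients still event-free at the time point, and set the cut-off as the largest count with about 9% or less probability at 70% for the actual evaluable number (for example 47 of 76, 52 of 83, or 60 of 95 at 2 years).
5. Replace 81% / 9% with the figures for the method chosen. For the time-to-event example at five years, simulation (110 patients, 10 a year, EFS 69% or 75%, onset shapes 0.7 to 1.5) gives 8-9% error. Power is about 65-72% if the analysis waits only for the 2-year minimum, and about 71-75% if it waits until the last patient reaches five years.

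The cost is rewording and a short recalculation, with no added patients or data. The stated power becomes less favourable, and waiting for five years on the last patient would put the analysis up to three years later.

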**Schedule of Assessments:**

Data Set	Completed prior to enrollment or within 35 days after enrollment	Weekly Visit During RT	At least 1 visit after RT within 3 months (suggested = 6 weeks after RT)	Yearly Follow-Up (+/- 6 months)
Age	x			x
Sex	x			
Hx and P	x	x	x	x
Acute Toxicity Assessment		x	x	

Bone Marrow Biopsy at diagnosis for intermediate and high-risk patients	x			
PET or Bone scan	x			
Chest CT at diagnosis	x			
CT or MRI of the original site of disease (plain film if it is an extremity), at diagnosis	x			x (per IRS guidelines)
Brain MRI or CT if parameningeal, at diagnosis	x			
Late Toxicity Assessment				x
Site related tests that will be repeated at yearly f/u (see below).	x			x

**Note:** Many patients have received surgery and chemotherapy prior to being referred for radiation therapy. The timing of the radiation therapy is dictated by the treatment protocol or by best clinical judgment. Some patients who are very young at diagnosis (such as <1 year old) are treated off-protocol and given the full 48 weeks of chemotherapy prior to their radiation therapy in order to allow maximal growth and development before radiation therapy.

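### The two dose groups for analysis both include 45 Gy, one of the four typical doses, and the plan does not say where those patients are counted

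*Combined protocol and SAP*

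**What the plan says.** Section VI names acute and late complications as the primary outcomes. It then explains that doses differ with tumor characteristics, lists them ("typical doses are 36 Gy, 41.4 Gy, 45 Gy and 50.4 Gy"), and says in the same sentence that "the outcomes will be analyzed according to dose group, $\leq$ 45 Gy and $\geq$ 45 Gy".

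Two further sentences bear on the split. One describes patients already enrolled: "Data on the enrolled patients shows a 1:4 ratio in the distribution of patients receiving low versus intermediate radiation doses". The other names particular outcomes for this analysis: "Constitutional symptoms, namely fatigue and malaise, as well as skin reactions in the radiation port will be analyzed according to dose group".

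Section V (Dose Specification and Schedule) gives the same four doses: "Typical doses are 36 Gy, 41.4 Gy, 45 Gy and 50.4 Gy depending on the circumstances". It attaches no analysis grouping to them. No other part of the supplied text gives a cut-point for analysis.

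**The concern.** A grouping rule should place each patient in exactly one group. This one does so for every dose except its own boundary, and the boundary is a dose the protocol expects to deliver.

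That leaves two ways to carry out the analysis, neither satisfactory. Read literally, 45 Gy patients contribute to both sets of results. The groups are then not independent, and any contrast between them is blurred. Alternatively, the analyst chooses a side. The choice is not in the plan, could be made after toxicity by dose has been seen, and cannot be reproduced by a reader.

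The sentence covers the outcomes generally, and fatigue, malaise and skin reactions in the radiation port are named individually. What is at stake is how clear and reproducible those dose-group summaries are. No test, precision target or decision is attached to them.

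**Working it through.** **Inputs.** From Section VI: the groups d ≤ 45 and d ≥ 45; the doses 36, 41.4, 45 and 50.4 Gy (repeated in Section V); the 1:4 ratio; 110 patients in the late-effect rule; accrual goal 115. The number of patients at each dose is not given.

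**The plan's own figures.** The 1:4 ratio is the only figure attached to dose level. It cannot be reproduced without counts by dose. As a check on the rest of the section, the exact binomial gives P(X ≤ 70 | n = 110, p = 0.60) = 0.809 against the stated 81%, and P(X ≤ 70 | n = 110, p = 0.70) = 0.0897 against the stated 9%. Both reproduce, and neither uses dose group.

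**Membership as printed.**

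| Dose (Gy) | d ≤ 45 | d ≥ 45 |
|---|---|---|
| 36 | yes | no |
| 41.4 | yes | no |
| 45 | yes | yes |
| 50.4 | no | yes |

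That is 3 + 2 = 5 memberships for 4 doses. The excess of one is 45 Gy.

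**What the ratio can and cannot show.** A 1:4 ratio means 1/5 = 20% low and 4/5 = 80% intermediate. On 110 patients that is 22 and 88; on 115 it is 23 and 92. Let r be the share of patients treated to exactly 45 Gy, and suppose that each patient was tabulated once at a 45 Gy cut.

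- If 45 Gy was counted as intermediate, 0 ≤ r ≤ 80%, and the printed groups hold (20% + r) and 80%.
- If 45 Gy was counted as low, 0 ≤ r ≤ 20%, and the printed groups hold 20% and (80% + r).

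Either way the printed groups sum to 100% + r. If the tabulation used some other cut, it gives no bound on r.

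**Illustration with assumed values of r.** On 110 patients the printed groups would total 110 × (1 + r): 121 at r = 10%, 132 at 20%, 154 at 40%. If 45 Gy had been counted as intermediate, moving those patients to the lower group would take it from 22 to 22 + 110r: 33, 44 and 66 at the same three values. With r near zero almost nothing changes. The documents do not say which applies.

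**Late effects.** Numbers by dose are not available here either. Section VI removes patients from evaluation after several events ("Patients will not be evaluable for late effects following treatment failure in local, regional and/or metastatic sites", and also second malignancy or death), so the evaluable count at each dose would differ from the treated count.

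**Is the sign a reading error?** The text was extracted from PDF, and the original page was not available. Strict signs do survive elsewhere in the same text: in Section VI ("delayed effects attributable to radiation which occur > 90 days following completion of radiation"), in the note to the Schedule of Assessments in Section IV ("Some patients who are very young at diagnosis (such as <1 year old) are treated off-protocol"), and in the size key under the staging table in Section I, where a strict sign stands beside an inclusive one. A misread is therefore possible but not shown.

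**The case against.** The strongest reply has three parts.

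First, the evidence is one character. The surviving strict signs are plain keyboard characters, whereas the disputed pair comes through as mathematical markup. Their survival shows that strict signs are not always converted; it does not verify this pair. That stands, and it is why the source page must be checked. The staging key, which has an inclusive sign in markup next to a plain strict one, gives some support to the printed reading.

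Second, no sensible analyst would count a patient twice. The ratio of low to intermediate doses follows directly after the groups, and a ratio implies that each patient was counted once. The text names no cut other than 45 Gy, so the natural reading is a disjoint split with a slip in one sign. This is fair and makes literal double counting the less likely outcome. It does not say on which side of the slip 45 Gy belongs, so the reproducibility gap remains.

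Third, nothing that drives the trial depends on dose group, and the bounds on r are too wide to inform. Section VI itself warns that subgroup analysis of acute symptoms may be confounded by concurrent chemotherapy. All of this is correct. It limits the weight of the point but does not remove it.

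**Conclusion.** The concern holds. As printed, the groups overlap at a dose in use, and nothing in the supplied text assigns those patients. The rule is wrong as written, rather than merely short of detail.

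The numerical effect is unknown because the count at 45 Gy is not given; the figures for assumed shares above are illustrations, not estimates. The consequence is confined to results reported by dose group. The 70-of-110 rule, the accrual goal and the precision stated for parameningeal and orbital tumors are untouched.

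The conclusion assumes that the extracted signs match the source page. If that page shows a strict sign, the overlap disappears, although low and intermediate would still be undefined in Gy. Confidence is medium for this reason. The correction should be made, on grounds of reproducibility and low cost.

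**What to change.** 1. Check the source page for a strict sign.
2. If both signs are inclusive, make one strict. The groups then become either {36, 41.4} against {45, 50.4}, or {36, 41.4, 45} against {50.4}.
3. Define low and intermediate in Gy so that they match the groups.
4. If the 1:4 tabulation used a 45 Gy cut, place 45 Gy on the side used there. If it did not, choose a side and restate the ratio.
5. Do this before outcomes are analysed by dose.

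The cost is one sign and one defining phrase in Section VI, plus at most a retabulation of enrolled patients by dose. Accrual, data collection and the decision rule do not change. The correction concerns analysis grouping only and takes no position on any prescribed dose.
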